## 2 Study Objectives and Design

### 2.1 Study objectives

To determine efficacy and safety of MONOBLUE DUAL View and MONOBLUE ILM View (study products) vital stains during vitrectomy surgery

Both study products are CE-marked and legally marketed in Europe. The data collection will serve as Post-Marketing Clinical Follow-up according MDR provisions. Retrospective data will also be collected for the two reference products: ILM Blue® (DORC) and Membrane Blue Dual® (DORC) to serve as control. For this purpose, patient data will be used that were collected in studies S61408 (Comparative study 23G vs 27G vitrectomy), S63610 (Comparative study 27G vitrectomy vs larger gauge surgery) and S64913 (EVA Nexus Field Observation Study).

The expected effect of the study products is to provide the retinal surgeon with adequate aid in visualizing the membranes involved in the retinal pathology to treat, thanks to their staining capabilities. The performance of the study products is related to the visualization of retinal tissues (ILM and/or ERM) during the vitrectomy procedure, when these tissues cannot be distinguished accurately enough without staining. Their use allows for better identification of these tissues and facilitates their removal by the surgeon. The clinical benefit of using ophthalmic dyes is to increase the patient's ability to recover anatomically and functionally by allowing more precise surgery with an effective visualization tool.

Along with collecting post-marketing clinical follow-up data on the subject products, the outcomes of the present study results may be used at the UZLeuven Hospital to decide to use Monoblue ILM View and/or Monoblue Dual View as standard-of-care, replacing Membrane Blue Dual and ILM Blue.

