### 2.2 Primary Endpoints

Efficacy: visualization of membranes stained based on binary subjective evaluation.

Assessment of efficacy (success) is provided in section 3, Study Endpoints. |

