### 2.3 Secondary Endpoints

- Efficacy: subjective assessment of surgical help provided by the product
- Safety:
  - Rate and severity of potential study-related products adverse events
  - Visual outcome at the last postoperative visit

The study hypothesis to be verified is non-inferiority in term of efficacy between study products and comparator based on a binary subjective evaluation of visualization of membranes stained. The proportion of success between study products and comparator will be studied, covariates (age, gender, visual acuity in the affected eye, surgery type being vitrectomy or phaco plus vitrectomy) taken into using a propensity score methodology.

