## 4 Statistics and Data Analysis

The primary outcome of the study is the success of the products based on assessment of efficacy of the staining dye.

Safety of the dye will be assessed by comparing the surgical outcome of the patients to a similar control group that underwent surgery using the staining dyes presently used in our department (see study endpoints).

Statistical analyses will be performed with R version 3.6.2 or higher. In case of missing values, the underlying missingness process (MCAR, MAR or MNAR) will be investigated and 15 multiple imputations will be performed using the **MICE** R package.

We will test with the statistical test of Jamshidian and Jalal (2010), implemented in the **MissMech** R Package (Jamshidian, Jalal & Jansen, 2014), whether missing data were MCAR. If they were not MCAR, we investigated whether or not the missing mechanism could be explained by baseline characteristics (eg, sociodemographic, medical features) of patients using logistic regression, which would suggest an MAR mechanism. If missing data were not MCAR or MAR, they were considered as MNAR.

For each dataset created, two propensity scores will be performed: a first one between the Monoblue ILM View and the ILM Blue, and a second one between the Monoblue Dual View and Membrane Blue Dual. The next covariates were selected for the propensity score: age, gender, visual acuity of the affected eye, surgery type of the affected eye (vitrectomy only vs phaco and vitrectomy). The Covariate Balancing Propensity Score provided in the R **CBPS** package (Imai & Ratkovic, 2014) will be used to estimate an Average Treatment Effect (ATE). The ATE will be estimated by covariate balancing and requesting an exact match. An absolute standardized difference less than 10–15% will be considered to support the assumption of balance between the groups. Unlike the P-value, this method is not affected by the sample size, and it could be used to compare the relative balance of variables that were measured in different units (Austin, 2011). Results (obtained after matching) will be expressed as the mean and standard deviation (SD) for continuous variables or the percentage for categorical variables. The **survey** R package will be used to perform linear regressions for continuous outcome variables and logistic regressions for binary variable. These regressions

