will include the treatment group effect, the weight resulting from the matching, and variables present in the propensity score. This procedure will provide a doubly-robust estimator, which corrected the last remaining possible imbalance between the covariates and produced an unbiased treatment effect (Funk et al., 2010). We will then combine results of the 15 regressions by taking the mean of the estimates of the regression coefficients of the treatment effect and the its associated p-value for each imputed dataset (the so-called, 'Mite approach'), as described by Leyrat et al. (2019). Adjusted P-values less than 0.05 will be considered significant.

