**Primary endpoint: Study product efficacy (success, defined as follows):**

From the surgical report, the following data will be extracted:

1. In case of surgery for macular hole or vitreomacular traction:

- A. Was the staining of the ILM satisfactory to initiate the peeling: yes / no
- B. Was the staining of the ILM satisfactory to create the ILM rhexis: yes / no
- C. Was it necessary to use another vital dye in order to obtain satisfactory staining: yes / no

Success is defined as answer “yes” to 1.A and/or 1.B

2. In case of surgery for macular pucker:

- A. Was the staining of the ERM satisfactory for its removal: yes / no
- B. In case the ILM was removed separately from the ERM:
  - i. Was the staining of the ILM satisfactory to initiate the peeling: yes / no
  - ii. Was the staining of the ILM satisfactory to create the ILM rhexis: yes / no
- C. Was MONOBLUE DUAL View repeatedly injected: yes / no
- D. Was it necessary to use another vital dye in order to remove the ERM: yes / no
- E. Was it necessary to use another vital dye in order to remove the ILM: yes / no

Success is defined as “yes” answer to 2.A and 2B.i or 2B.ii

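### Surgeon is missing from the covariates although the primary endpoint is a subjective judgement from the surgical report; if several surgeons took part in unequal mixes, their differences would read as a dye effect

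*Combined protocol and SAP*

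**What the plan says.** Section 2.2 defines the primary endpoint as "Efficacy: visualization of membranes stained based on binary subjective evaluation". Section 5.2 gives the source: "From the surgical report, the following data will be extracted". A typical item is "Was the staining of the ILM satisfactory to initiate the peeling: yes / no". No independent or masked reader is described.

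The covariates are fixed in two places and agree. Section 2.3 has "covariates (age, gender, visual acuity in the affected eye, surgery type being vitrectomy or phaco plus vitrectomy) taken into using a propensity score methodology". Section 4 lists "age, gender, visual acuity of the affected eye, surgery type of the affected eye (vitrectomy only vs phaco and vitrectomy") for both propensity scores, one for each study product against its comparator. The outcome regressions "will include the treatment group effect, the weight resulting from the matching, and variables present in the propensity score". Section 4 then says that this doubly robust procedure gives an unbiased treatment effect.

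The two sides of each comparison come from different places. Section 1 says that samples of both study products were obtained from the manufacturer for a demonstration approved at the hospital. For the controls, section 2.1 says "patient data will be used that were collected in studies S61408 (Comparative study 23G vs 27G vitrectomy), S63610" and a third study, S64913. Section 4 describes the controls only as a similar group treated with the dyes the department now uses.

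**The concern.** When an endpoint is an opinion, the threshold of the person giving it is part of the measurement. Surgeons can differ in what they call satisfactory staining and in how much stain they need. All four covariates describe the patient or the procedure; none describes the rater.

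Separate sourcing of study-product and control eyes makes an unequal surgeon mix possible. If it occurred, a difference between surgeons would be credited to the dye. The plan's balance check (absolute standardized difference below 10–15%) would not reveal it, because it is applied to the listed covariates only.

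The error could go either way, so it could create or hide non-inferiority. Section 2.1 says the results may be used to decide whether the hospital replaces its present dyes.

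**Working it through.** **No figure to reproduce.** The documents state no sample size, margin, expected success rate or number of surgeons. The check is therefore a comparison of the text followed by a hypothetical calculation.

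**Step 1: is surgeon in the adjustment?**
- Section 2.3: age, gender, visual acuity, surgery type.
- Section 4, propensity scores: the same four.
- Section 4, outcome regression: treatment group, weight, the same four.

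Surgeon is not a covariate, stratum, random effect or cluster in any of these.

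**Step 2: does the doubly robust step help?** It protects against a misspecified propensity or outcome model for the covariates included. Both models here use the same four variables, so a confounder outside the list is controlled only so far as it is related to them.

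**Step 3: how large could the effect be?** Take two surgeons, A and B, and no true dye effect. All inputs below are assumptions.
- pA, pB: the proportion of eyes each surgeon calls satisfactory.
- sT, sC: surgeon A's share of study-product and control eyes.
- Surgeon is unrelated to the four covariates, so weighting leaves the shares as they are.

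Expected success with a dye is s·pA + (1 − s)·pB, so

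spurious difference = (sT − sC) × (pA − pB).

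| pA | pB | sT | sC | Calculation | Spurious difference |
|---|---|---|---|---|---|
| 95% | 90% | 70% | 30% | 0.40 × 0.05 | 2 points |
| 95% | 85% | 70% | 30% | 0.40 × 0.10 | 4 points |
| 95% | 85% | 90% | 30% | 0.60 × 0.10 | 6 points |
| 98% | 80% | 100% | 50% | 0.50 × 0.18 | 9 points |
| 98% | 80% | 50% | 100% | −0.50 × 0.18 | −9 points |
| any | any | 100% | 100% | 0 × (pA − pB) | 0 (one surgeon) |

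The difference is also zero when sT = sC or pA = pB.

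**Step 4: would the plan's balance rule catch it?** For shares of 70% and 30%, the standardized difference is (0.70 − 0.30)/√[(0.70×0.30 + 0.30×0.70)/2] = 0.40/√0.21 = 0.40/0.458 = 0.87. That is 87% against a limit of 10–15%, but it would go unseen because surgeon is not among the variables checked.

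**The case against.** The strongest objection is that the bias needs three things together: more than one surgeon, surgeons with different thresholds, and a mix that differs by dye. None is documented. The study-product eyes come from a demonstration, the synopsis has a single principal investigator entry, and all the dyes compared belong to one hospital's practice. One operator, or the same operators on both sides, fits the text. The pages listing participating sites were removed before review, so missing operator details there cannot be held against the plan. This objection stands, and it is why the point is conditional.

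A reader might infer more in three ways, none supported:
- **That surgeon and dye are confounded here.** Separate sourcing makes a different mix possible; it does not show one.
- **That the result is off by 2 to 6 points.** Every rate and share behind that figure is assumed, and there is no stated margin to compare it with.
- **That surgeon is not recorded.** The lists in section 5.2 cover endpoint items only. Age, gender and surgery type are not listed there either, yet they are clearly to be used.

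That the rater is the operating surgeon is also an inference from the use of the surgical report. It is the natural reading but is not stated.

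A further objection concerns the remedy. Section 4 targets an average treatment effect with exact balance. A surgeon who used only one of two dyes has a treatment probability of 0 or 1, so forcing surgeon into the score could give extreme weights or no solution. This also stands, and the fix needs an overlap rule.

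What the objections do not remove is the omission itself: the covariate list is closed, it leaves out the rater, and no passage says that one surgeon did every case.

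**Conclusion.** The point holds in conditional form. The plan adjusts a subjective endpoint for patient and procedure variables but not for surgeon. If several surgeons with different thresholds contributed in different proportions to the two dyes of a comparison, the planned analysis would attribute part of that difference to the dye. The statement that the estimate is unbiased does not cover that case.

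The size is unknown. It is zero with one surgeon, equal mixes or equal thresholds. The assumed scenarios run from 0 to about 9 points in either direction and show only how the bias scales. The conclusion rests on two assumptions: that the operating surgeon gave the yes/no answers, and that there was more than one surgeon. Both can be settled from the surgical reports before analysis.

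**What to change.** Extract a coded surgeon identifier from each surgical report, and tabulate surgeon by dye separately for Monoblue ILM View against ILM Blue and for Monoblue Dual View against Membrane Blue Dual. Then, for each comparison:

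- **One surgeon in all:** say so in section 4 and change nothing else.
- **More than one, with overlap:** add surgeon to the propensity score, the balance check and the outcome regression, pooling surgeons with few cases. Restrict this surgeon-adjusted analysis to surgeons who used both dyes of the comparison.
- **No overlap:** do not force the term. Report that surgeon and dye cannot be separated, and withdraw the claim of an unbiased effect.

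The cost is one eCRF field, a few degrees of freedom, and some loss of precision or of eyes where overlap is limited. In the restricted analysis, the estimate then applies to the overlapping surgeons' patients only. The change does not deal with unmasked rating, where even a single surgeon who knows the dye may judge a new product differently, or with differences in calendar time between study and control eyes.

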## STUDY SYNOPSIS

Title of clinical Study («Study»)	Efficacy and safety evaluation of MONOBLUE DUAL View and MONOBLUE ILM View vital stains during vitrectomy surgery
Protocol Short Title Acronym	NewBlueDyes
Sponsor name	University Hospitals Leuven (UZ Leuven)>
Principal Investigator	[name]. [name]
Contact Address PI	UZ Leuven, [name]
Contact Email PI	[contact]
Contact Phone PI	[name]
Other public database nbr	NA
Coordinating Investigator	NA
Medical devices	Monoblue Dual View Monoblue ILM View
Study rationale	Retrospective Data Collection
Primary objective	Efficacy: visualization of membranes stained based on binary subjective evaluation.
Secondary objective(s)	

• Efficacy: subjective assessment of surgical help provided by the product

• Safety:

○ Rate and severity of potential study-related products adverse events

○ Visual outcome at the last postoperative visit

Endpoints	Effectiveness Outcomes: Improvement in BCVA after 2 months as compared to preoperative BVCVA. Safety Outcomes: Safety will be assessed based on incidence and severity of investigational device-related adverse events.
Time frame of collecting data for retrospective analysis	SEPTEMBER 2021-APRIL 2022

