**Secondary endpoint: assessment of surgical safety**

The following endpoints will be used to determine surgical safety:

- Occurrence of adverse events during or after the surgery, whereby both treatment groups will be compared to the corresponding control groups (see above). Occurrence of adverse events will be collected over the duration of the study and up to week 6-10 postoperative, and will be assessed cumulatively.
- Visual outcome at the last postoperative visit, i.e. week 6-10 after the surgery

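### Coding surgery type in two levels leaves lens status unadjusted, so a different lens mix between dye groups could appear as a dye effect on acuity at week 6–10

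*Combined protocol and SAP*

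**What the plan says.** Section 4 (Statistics and Data Analysis) builds one propensity score for each pair of dyes from age, gender, preoperative acuity and "surgery type of the affected eye (vitrectomy only vs phaco and vitrectomy". Section 2.3 gives the same four covariates, with "surgery type being vitrectomy or phaco plus vitrectomy". The outcome regressions add nothing further: they "will include the treatment group effect, the weight resulting from the matching, and variables present in the propensity score". Balance is accepted when standardized differences fall below 10–15%.

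The outcome at issue is in section 5.2, under surgical safety: "Visual outcome at the last postoperative visit, i.e. week 6-10 after the surgery". The synopsis also lists acuity, under effectiveness: "Improvement in BCVA after 2 months as compared to preoperative BVCVA". On the comparison itself, section 4 states: "Safety of the dye will be assessed by comparing the surgical outcome of the patients to a similar control group". Section 2.1 draws the controls from three other studies: two gauge comparisons and one field observation study.

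Neither the eligibility criteria (sections 3.1 and 3.2) nor the data items listed in section 5.2 mention lens status or cataract.

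**The concern.** By adjusting for combined phaco surgery, the plan accepts that the lens matters to the outcome. The two-level variable captures only part of that. Eyes without phaco can be of two kinds: eyes that keep their natural lens, where opacity can limit acuity, and eyes that already have an artificial lens, where it cannot. Both the propensity score and the regression treat the two kinds as exchangeable, given age, gender and preoperative acuity.

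The controls were not randomised against the study dyes, so nothing in the design makes the lens mix equal. A difference in mix could produce a false safety signal or hide a real one. Section 2.1 says the results may inform whether the hospital replaces its current dyes, so the visual comparison could carry weight even though it is secondary.

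**Working it through.** The plan states no sample size, SD, lens mix or expected acuity difference, so there is no figure of its own to reproduce. The steps below test the mechanism and show a range.

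**1. Where each eye falls under the planned coding**

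| Eye before surgery | Surgery | Level of the covariate |
|---|---|---|
| Phakic | Phaco and vitrectomy | Combined |
| Phakic, lens kept | Vitrectomy | Vitrectomy only |
| Pseudophakic | Vitrectomy | Vitrectomy only |

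The third row follows from the definition, because phaco is not possible in a pseudophakic eye. How many eyes fall in the second row is not stated.

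**2. Formula**

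Bias in the overall dye estimate = (share of eyes that are vitrectomy only) × (difference in phakic share within that class) × (lens effect on acuity, given the other covariates).

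**3. Inputs, all assumed**

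- Vitrectomy-only share: 0.60
- Difference in phakic share: 0.20 to 0.40
- Lens effect: 0.05 to 0.20 logMAR
- SD: 0.25 logMAR
- Eyes per group: 40
- One letter: 0.02 logMAR

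**4. Result**

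- Low end: 0.60 × 0.20 × 0.05 = 0.006 logMAR (0.006/0.02 = 0.3 letters).
- High end: 0.60 × 0.40 × 0.20 = 0.048 logMAR (0.048/0.02 = 2.4 letters).
- Standard error over all eyes: 0.25 × √(2/40) = 0.056.
- Ratios: 0.006/0.056 = 0.1 and 0.048/0.056 = 0.86.

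Within the vitrectomy-only class alone (0.60 × 40 = 24 eyes per group):

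- Bias: 0.20 × 0.05 = 0.01 to 0.40 × 0.20 = 0.08 logMAR.
- Standard error: 0.25 × √(2/24) = 0.072.
- Ratios: 0.01/0.072 = 0.14 and 0.08/0.072 = 1.1.

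**5. Simulation of the planned estimator**

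The simulation used exact-balance covariate-balancing weights for the ATE, then a weighted regression on treatment and the covariates. Missing data and imputation were left out. Assumed inputs: 100 eyes per group, residual SD 0.20, 60% vitrectomy only, phakic share in that class 40% against 70%, no true dye effect, 1,500 runs per setting.

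| Lens effect (logMAR) | Covariates | Mean estimated dye effect (logMAR) | p < 0.05 |
|---|---|---|---|
| 0.10 | planned four | 0.018 | about 10% |
| 0.10 | plus lens status | about 0.000 | 4.9–5.5% |
| 0.20 | planned four | 0.034–0.036 | 19–21% |
| 0.20 | plus lens status | about 0.000 | 5.1–5.3% |

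The formula agrees: 0.60 × 0.30 × 0.10 = 0.018 and 0.60 × 0.30 × 0.20 = 0.036. The ranges cover two settings: lens status unrelated to age and baseline acuity, and phakic eyes 5 years younger and 0.05 logMAR worse at baseline. The second removed only a small part of the bias. With an equal lens mix the bias was 0.0001 and the rejection rate 5.9% under the planned covariates.

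**6. What the balance check sees**

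Under the planned covariates and the unequal mix, weighting balanced surgery type exactly (weighted difference 0.000). A difference of 0.17–0.18 in the overall phakic share remained. The planned check would have passed.

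**The case against.** The strongest reply is that neither the lens mix nor the lens effect is in the documents. If phakic eyes at this site usually had combined surgery, the vitrectomy-only class would be almost entirely pseudophakic and the problem would largely vanish. Section 2.1 does not define the control studies by lens status, and section 4 says the control dyes are those now used in the same department, which suggests similar practice. Age and preoperative acuity are adjusted for twice and may absorb part of any effect. The exclusion in section 3.2 of other eye disease that could affect the surgical result might be read to remove marked lens opacity. Any observational plan can be asked for one more covariate.

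Most of this stands as a limit on size. It does not remove the mechanism. The section 3.2 exclusion does not name cataract and would not separate phakic from pseudophakic eyes. Adjustment for age and acuity helps only as far as they predict lens status. This covariate also differs from an arbitrary extra one, because it completes a factor the plan already chose to adjust for.

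Four stronger readings are tempting but unsupported:

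- A reader might infer that the visual comparison is biased. The documents show only that it could be, and the direction is unknown.
- A reader might divide 0.08 by 0.056 and infer a bias of 1.4 standard errors. That sets a bias within vitrectomy-only eyes against a standard error for all eyes. It would hold only if every eye were vitrectomy only and both assumed ranges were at their extremes.
- A reader might take the absence of lens status from section 5.2 as proof that it will not be collected. That list also omits age and gender, which the analysis needs. The telling omission is from the covariate lists in sections 2.3 and 4.
- A reader might assume that lens status is in the surgical report or the control datasets. Neither is stated.

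**Conclusion.** The point holds as a conditional one. The two-level covariate would pool pseudophakic eyes with any phakic eyes whose lens is kept. An unequal mix could then enter the acuity comparison at week 6–10 without being seen by the balance check. Section 4 expects its doubly robust procedure to give an unbiased effect, but that property does not cover a covariate missing from both models.

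The size cannot be set from the documents. On the assumptions above it runs from negligible (0.1 standard errors) to a bias nearly as large as the standard error (0.9). It is zero if the lens mix is equal, or if lens status has no effect at week 6–10 given the other covariates. The point concerns the visual outcome only, not the binary staining endpoint on which the non-inferiority hypothesis rests. It is a cheap improvement and not a flaw that undermines the study.

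**What to change.** Extract preoperative lens status for study and control eyes from the medical record where available. First check whether the three control datasets hold it, since the documents do not say.

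For the visual outcome, replace the two-level covariate by three levels in the propensity score, the outcome regression and the balance table:

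- phakic, lens kept
- pseudophakic
- phaco plus vitrectomy

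If lens status is incomplete, or a level is too sparse for exact balancing, keep the planned covariate and report the visual outcome by lens class as a sensitivity analysis. If a control study holds no lens data at all, state that as a limitation of the visual comparison.

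The cost is one extra extracted item and one extra parameter per dye comparison. The weights will be somewhat more variable in small groups. How much more cannot be judged without a stated sample size.

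### The planned survey-package logistic test nearly always declares significance when exactly one dye group has no adverse event, or no staining failure, even at 0 versus 1

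*Combined protocol and SAP*

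**What the plan says.** Section 4 sets one method for every binary outcome, using the survey package in R: the "R package will be used to perform linear regressions for continuous outcome variables and logistic regressions for binary variable". On the content of each model, the plan adds that it "will include the treatment group effect, the weight resulting from the matching, and variables present in the propensity score". The covariates are "age, gender, visual acuity of the affected eye, surgery type of the affected eye (vitrectomy only vs phaco and vitrectomy"), and on the weights the plan says "The ATE will be estimated by covariate balancing and requesting an exact match". Results over 15 imputed datasets are combined through "the mean of the estimates of the regression coefficients of the treatment effect and the its associated p-value for each imputed dataset". The decision rule is "Adjusted P-values less than 0.05 will be considered significant".

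The safety endpoint under section 5.2 is "Occurrence of adverse events during or after the surgery, whereby both treatment groups will be compared to the corresponding control groups". There are two comparisons: "a first one between the Monoblue ILM View and the ILM Blue, and a second one between the Monoblue Dual View and Membrane Blue Dual". Success or failure of staining, the primary endpoint, is also binary.

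The plan has no rule for a group with no events, and no exact test, penalised fit or minimum event count. It gives no sample size and no expected adverse-event rate.

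**The concern.** When one group has no events, the maximum-likelihood log odds ratio is infinite, and the software reports whatever value the iterations had reached. An ordinary model-based standard error becomes huge at that point and gives p near 1. The design-based standard error does not. It is built from residuals, and in the event-free group these shrink as fast as the fitted risk. The coefficient runs away while its standard error stays near 1, so p collapses towards zero. The test then detects an empty cell, not a difference in risk.

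One chance event in a control group and none in the Monoblue group would come out as a significant safety advantage, and the reverse as significant harm. The primary endpoint is exposed in the same way if one dye has no failures. Section 2.1 says the results may inform whether the hospital replaces its current dyes.

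**Working it through.** **Inputs.** From the plan: survey-package logistic regression, treatment plus four covariates, exactly balancing weights for the average treatment effect, threshold 0.05, two comparisons. Assumed, because the plan gives none: group sizes, event risks, covariate distributions and a two-sided test. The plan has no figure to reproduce.

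**1. Standard error, treatment-only model with unit weights.** For a group of n eyes with fitted risk p, the linearised variance of the log odds is Σ(y − p)² / [n p(1 − p)]².
- Group with events (fitted risk equals observed risk): 1 / [n p(1 − p)].
- Event-free group with fitted risk ε close to 0: nε² / [nε(1 − ε)]² ≈ 1/n.

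**2. Example, 0/30 versus 1/60.**
- Variance: 1/30 + 60/59 = 0.0333 + 1.0169 = 1.0503. Times n/(n − 1) = 90/89, this is 1.0621, so SE = 1.03.
- With R's default convergence rule the coefficient stops at −17.49.
- t = −17.49/1.03 = −17.0 on 88 df, so p is about 1e-29.
- Fisher: a single event falls in the group of 60 with probability 60/90 under equal risk. This is the likelier split, so the two-sided p = 1.0.

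**3. Neighbouring tables, same method.**

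| Events | Planned p | Fisher p |
|---|---|---|
| 0/50 vs 1/50 | about 1e-31 | 1.0 |
| 0/50 vs 2/50 | about 2e-44 | 0.495 |
| 1/50 vs 2/50 | 0.57 | 1.0 |
| 1/50 vs 4/50 | 0.21 | 0.36 |

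So 0 versus 1 is overwhelmingly significant and 1 versus 4 is not. For 0/50 versus 1/50 the model-based SE is about 6,800, so an ordinary Wald test gives t = 17.67/6,800 = 0.003 and p near 1. Swapping events and non-events only changes the coefficient's sign, so the primary endpoint behaves identically when one group has no failures.

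**4. Full model.** With four simulated covariates and exactly balancing weights (300-400 datasets per setting):
- 0 versus 1: p < 0.05 in 96-99% of datasets with 20-100 eyes per group, and in 100% with 200.
- 0 versus 2: 99-100%.
- 0 versus 3 or more: 99.7-100%.

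**5. How often the pattern arises under equal true risk r.** With n eyes per group and q = (1 − r)^n, the chance that exactly one group is empty is 2q(1 − q). For n = 50 and r = 2%: q = 0.98^50 = 0.364, and 2 × 0.364 × 0.636 = 0.46.

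| Eyes per group | 1% | 2% | 5% | 10% |
|---|---|---|---|---|
| 30 | 0.39 | 0.50 | 0.34 | 0.08 |
| 50 | 0.48 | 0.46 | 0.14 | 0.01 |
| 100 | 0.46 | 0.23 | 0.01 | <0.001 |

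Overall rejection rates simulated under the full model (600 runs per setting; 20 vs 40 and 30 vs 30 up to 50 vs 100 eyes) were 40-55% at 1% risk, 38-58% at 2%, 11-42% at 5% and 3-15% at 10%.

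**6. Imputation and adjustment.** If the outcome is complete, all 15 datasets contain the same empty cell, so averaging 15 p-values near zero leaves the average near zero. No usual multiplicity adjustment matters at 1e-29.

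**7. The remedy on the same example.** For a two-group table, Firth's penalty adds ½ to each cell. The odds ratio is (0.5 × 59.5)/(30.5 × 1.5) = 0.65. The penalised likelihood-ratio statistic is 2[0.5 ln(0.0161/0.0217) + 30.5 ln(0.9839/0.9783) + 1.5 ln(0.0246/0.0217) + 59.5 ln(0.9754/0.9783)] = 0.073 (from unrounded values) on 1 df, so p = 0.79.

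**Limit of the check.** The survey package itself was not available. Its calculation was rebuilt in Python and with R's glm plus the linearised variance, and the two agreed.

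**The case against.** **The route is inferred.** The plan does not use the word Wald and does not name logistic regression for adverse events; the endpoint is also described as rate and severity. This is true. But occurrence is binary, section 4 gives binary variables one method, and the coefficient's default p-value in that method is this test. The inference is reasonable, and no text points elsewhere.

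**The failure is not universal.** A reader might infer that every 0-versus-1 split is declared significant. With a single event and four covariates, about 1-4% of simulated datasets escape at up to 100 eyes per group.

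**Adverse events may not be rare.** Section 5.2 counts events cumulatively to week 6-10, which can be read as any event per patient. At 10% risk, rejection was 4-6% in three of four settings and 14% at 30 vs 30; at 20% it was 4-8%. This stands: a false-signal rate of 40% or more cannot be read as a property of the trial.

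**An analyst would notice.** An odds ratio near 1e-8 beside counts of 0 and 1 is conspicuous, and with a single event the fit converged in only 25-75% of datasets at 20-100 eyes per group. That may prompt a repair, but an unplanned one made after seeing the data.

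**Sparse counts in general.** A reader might infer that the planned model fails whenever a group has fewer than 5 events, and that Fisher's test should replace it. The checks do not support this. With at least one event in each group and fewer than 5 in one, rejection was 1-7% with weights (at 2-10% risk) and about 3-10% without. At 10% risk and 50 vs 50 eyes, a fewer-than-5 rule would apply 68% of the time, against 1% for exactly one empty group. An unadjusted test would also discard the confounding control that this non-randomised comparison relies on. In a deliberately strong illustration (surgery type 80% vs 40%, risk 20% vs 2% by surgery type, no dye effect, 50 vs 100 eyes), Fisher's test rejected in 21% of runs.

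**Conclusion.** The plan is wrong as written for a specific and plausible result: exactly one dye group with no adverse event, or with no staining failure. The planned p-value then falls below 0.05 in about 96-100% of datasets, whatever the evidence of a difference. This rests on the default design-based test of the survey package and on a complete outcome.

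Frequency rests on assumptions that the plan does not settle. Under equal true risks it is about 40-58% per comparison at 1-2% risk in most settings examined, about 10-40% at 5%, and near nominal at 10% (up to about 15% in the smallest groups). It falls as groups grow: with 100 eyes per group, the chance of exactly one empty group is 0.23 at 2% and 0.01 at 5%. The documents do not support reading this as a failure of the model for all low counts.

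**What to change.** Add a zero-cell rule to section 4:
- If either dye group has zero events, or zero non-events, on a binary outcome, the survey-package Wald p-value is not used. Judge this on the recorded outcomes, so that one method applies to all 15 imputed datasets.
- The main analysis is then a Firth-penalised logistic model keeping the propensity weights and/or the four covariates, with a penalised profile-likelihood confidence interval and p-value. If the weights are kept, rescale them to average 1, because a likelihood treats them as counts.
- Report the observed counts, with an unweighted risk difference, an exact or score 95% interval and Fisher's p as a descriptive supplement.
- Keep the planned model when both groups have at least one event and one non-event, and flag low counts.

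State that the rule covers the primary success endpoint as well as adverse events.

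The cost is a short paragraph and a few lines of R. Most zero-cell comparisons will be reported as inconclusive, which is what such data can support.
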